2.1.1.5 Follow up visit

Efficacy data collected at follow up visits will not be summarized.

Efficacy data collected at follow up visits will be listed.

2.1.1.6 Unscheduled visit

All safety and exposure to study treatment data collected at unscheduled visits will be summarized.

Efficacy data collected at unscheduled visits will be visit windowed as per section 2.1.1.4 and will be presented in the same manner as scheduled visits.

All data collected at unscheduled visits will be listed.

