2.1.1.4 Visit windows

Visit windows will be used for the data that is summarized by visit. They are based on the study evaluation schedule and comprise a set of days around the nominal visit day. For any assessment, there are the protocol defined scheduled visits around which visit windows were created to cover the complete range of days within the study. The visit windows in this study are shown in [Table 2-1](#). In this table, the days are counted since the first dose of study treatment. These visit windows apply to measurements taken at every visit. When visit windows are used, all visits (except follow up visits) will be re-aligned, i.e., they will be mapped into one of the visit windows. E.g., if the Week 4 visit of a subject is delayed and occurs on Day 46 instead of on Day 29, say, it will be re-aligned to visit window Week 8. If two visits fall into one window then the visit closest to target scheduled day will be analysed for that visit. Follow up visits will not be re-aligned.

Table 2-1 Assessment windows for scheduled visits

Visit	Week	Scheduled day	Visit Window
Baseline	0	1	-28 days to day 1
Visit 2	1	8	Day 2-11
Visit 3	2	15	Day 12-18
Visit 4	3	22	Day 19-25
Visit 5	4	29	Day 26-43
Visit 6	8	57	Day 44-71
Visit 7	12	85	Day 72-99

Visit	Week	Scheduled day	Visit Window
Visit 8	16	113	Day 100-141
Visit 9	24	169	Day 142-197
Visit 10	32	225	Day 198-253
Visit 11	40	281	Day 254-309
Visit 12	48	337	Day 310-351
Visit 13	52	365	Day 352-379
Extension 1	56	393	Day 380-421
Extension 2	64	449	Day 422-477
Extension 3	72	505	Day 478-533
Follow-up	80	561	≥ Day 534

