2.8.3 Laboratory data

The summary of the data for laboratory evaluations will be presented for both types of laboratory tests (hematology and biochemistry).

Descriptive summary statistics for the absolute values and changes from Baseline at each study visit will be presented. Descriptive summaries will be presented by type and by laboratory test.

For each parameter, shift tables will be produced in order to compare patient Baseline laboratory evaluation with the observed value at each visit. For these shift tables, the normal laboratory ranges will be used to evaluate whether a particular laboratory test value is normal, low, or high at each visit relative to whether or not the Baseline value was normal, low, or high. These summaries will be presented by laboratory test.

The expanded laboratory ranges and the clinically notable abnormalities of key laboratory tests are given in Appendix 9, Section 13.9 of the study protocol version 5.

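### Unscheduled laboratory values can drop out of every planned laboratory summary, because SAP 2.1.1.4, 2.1.1.6 and 2.8.3 are not reconciled and no table uses all post-Baseline results

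*SAP*

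**What the plan says.** Three sections of the SAP bear on the point.

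- **2.1.1.6 Unscheduled visit.** "All safety and exposure to study treatment data collected at unscheduled visits will be summarized". For efficacy it gives a method: "Efficacy data collected at unscheduled visits will be visit windowed as per section 2.1.1.4 and will be presented in the same manner as scheduled visits". It gives none for safety data. Everything from unscheduled visits is also listed.
- **2.1.1.4 Visit windows.** "Visit windows will be used for the data that is summarized by visit". Also: "When visit windows are used, all visits (except follow up visits) will be re-aligned, i.e., they will be mapped into one of the visit windows". Where two visits share a window: "If two visits fall into one window then the visit closest to target scheduled day will be analysed for that visit".
- **2.8.3 Laboratory data.** Descriptive statistics are given for each study visit, and "shift tables will be produced in order to compare patient Baseline laboratory evaluation with the observed value at each visit". The shift categories are low, normal and high by the normal ranges. On notable values the section says only where the criteria are found: "The expanded laboratory ranges and the clinically notable abnormalities of key laboratory tests are given in Appendix 9".

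For comparison, 2.8.4.2 Vital signs plans the number and percentage of subjects with notable values and flags them in the listing.

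**The concern.** The scope sentence of 2.1.1.4 is not confined to efficacy, and every laboratory summary in 2.8.3 is by visit. On its face, then, the one-visit rule reaches laboratory data. An unscheduled value farther from target than another visit in its window enters no laboratory summary, although 2.1.1.6 says that all such data are summarised. No worst-post-Baseline or any-time table would pick it up.

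The study is single-arm, so its laboratory safety evidence is descriptive frequencies. If unscheduled samples are abnormal more often than routine ones, losing them pulls those frequencies down. That is plausible, but the SAP does not say why unscheduled samples are taken.

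The unused notable-value criteria are a second gap, whatever the windowing rule. In a low/normal/high table, a value just outside the normal range and a clinically notable one fall in the same cell.

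**Working it through.** **1. The plan's own example.** In Table 2-1 the Week 8 window is Day 44-71, so a visit on Day 46 maps to Week 8, as 2.1.1.4 says. The windows from Day 2 to Day 533 are contiguous, so every unscheduled sample in that range falls into exactly one of them.

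**2. Following one unscheduled laboratory value through the text.**

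- *If 2.1.1.4 governs safety data:* the value is assigned to a window and kept only if its visit is the closest to target. Otherwise it is in no laboratory summary.
- *If 2.1.1.6 exempts safety data from windowing:* the value has no nominal week, and 2.8.3 has no table that is not by visit. If it is added to a by-visit shift table anyway, a patient can have two values at one visit, and no rule says which one defines the shift.

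Neither reading gives the programmer a workable instruction.

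**3. How often an unscheduled sample would lose under the first reading.** Inputs from Table 2-1: lower bound L, upper bound U and target day T. Assumptions: a scheduled sample lies in the same window, d days from target, and the unscheduled sample is equally likely on any day of the window. Ties are not counted as losses.

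Days farther from target = max(0, T - d - L) + max(0, U - T - d), divided by window length U - L + 1.

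For Week 16 with d = 7: (113 - 7 - 100) + (141 - 113 - 7) = 6 + 21 = 27 of 42 days, or 64%.

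| Window | L-U (T) | d = 0 | d = 3 | d = 7 |
|---|---|---|---|---|
| Week 4 | 26-43 (29) | 17/18 = 94% | 11/18 = 61% | 7/18 = 39% |
| Week 8 | 44-71 (57) | 27/28 = 96% | 21/28 = 75% | 13/28 = 46% |
| Week 16 | 100-141 (113) | 41/42 = 98% | 35/42 = 83% | 27/42 = 64% |
| Week 24 | 142-197 (169) | 55/56 = 98% | 49/56 = 88% | 41/56 = 73% |

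Weeks 12 and 52 have the same shape as Week 8. In the short early windows the loss is small: with d = 3 it is 3/10 = 30% in Week 1 and 0/7 in Weeks 2 and 3, where the outermost days tie.

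**4. Dependence on the laboratory schedule.** The SAP does not say at which visits laboratory samples are taken, so this was varied. One unscheduled sample was simulated on a random day from Day 2 to Day 533, with any scheduled sample at a random day within j days of target.

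| Assumed scheduled sampling | Share of unscheduled values dropped |
|---|---|
| Every window, all visits attended, j = 0 / 3 / 7 | 97% / 88% / 77% |
| Every window, 80% attended, j = 0 / 3 / 7 | 78% / 70% / 62% |
| Only 2 to 5 of the 15 post-Baseline windows, j = 3 | 11% to 35% |

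The sparse-schedule figures assume that an unscheduled value competes only with another laboratory value. The text of 2.1.1.4 selects a visit, not a non-missing value. Read literally, an unscheduled sample can lose to a nearer visit at which no blood was drawn, so sparse sampling does not clearly protect it.

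**5. Notable values.** Set side by side, 2.8.4.2 has a criterion, a patient-level count and a flag. Section 2.8.3 has a criterion only.

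**The case against.** The strongest reply is that 2.1.1.6 treats the two kinds of data differently on purpose. It sends unscheduled efficacy data to the windows and says nothing of the kind for safety data, so a fair reader may take safety data as exempt and nothing as lost. This has weight: the plan does not plainly contradict itself, and the defect is better described as rules left unreconciled. It does not remove the problem, because an exempt value still has no table in 2.8.3 to enter.

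A reader might also infer that the rule removes most unscheduled laboratory results. The document does not support that. The share depends on a sampling schedule that the SAP does not state, and 2.1.1.4 itself says "These visit windows apply to measurements taken at every visit", which laboratory tests may not be. Several windows give less than half even when a scheduled sample is present.

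Three further points stand. Listings keep every value. Adverse event summaries are not windowed, so an abnormality reported as an adverse event is counted there. The notable vital-sign count is already by patient and is not stated to be by visit, so vital signs do not share the full gap. By-visit shift tables are also a legitimate display in themselves; the difficulty is that they are the only one planned for laboratory categories.

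**Conclusion.** The point holds as an unreconciled rule with a practical consequence: under the current text, an abnormal unscheduled laboratory value can be absent from every planned laboratory summary and visible only in listings. Where a scheduled sample 7 days off target shares the window, the unscheduled one loses on about 39-46% of days at Weeks 4, 8, 12 and 52 and 64-73% at Weeks 16 and 24, with all days taken as equally likely. The overall share cannot be fixed from the SAP.

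Under-counting of abnormalities is a possible result, not a demonstrated one. It requires that the one-visit rule is applied to laboratory data and that the dropped values are abnormal more often than those kept. It is confined to laboratory summaries. The missing count of notable laboratory values does not depend on either assumption. The change should be made before database lock.

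**What to change.** - **2.1.1.4 and 2.1.1.6:** state that the closest-to-target rule applies only to by-visit displays.
- **2.8.3:** add a shift table from Baseline to the worst post-Baseline value, lowest and highest separately, and the number and percentage of patients with a newly occurring notable abnormality by the Appendix 9 criteria already cited. Both should use all scheduled and unscheduled results.
- **2.8.4.2:** no new table is needed; only clarify that the existing count of notable vital signs uses all post-Baseline results.

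The cost is one or two extra tables from data already collected, and possibly slightly higher abnormality counts. The by-visit tables stay as planned.

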2.2 Analysis sets

The following analysis sets will be used in this study:

Included Set (IS): The included set will comprise all patients included in the study. A patient is considered to be included in the study if he/she successfully completes the screening period. Completion of screening period is defined as patient who has “Will the subject continue into the Treatment phase?” equal to “Yes” from the *Screening Phase Disposition* eCRF page.

Full Analysis Set (FAS): The FAS will comprise all patients in the IS who are administered with at least one dose of investigational drug with at least one Baseline and one post-Baseline SPI evaluation.

The primary analysis will be performed on the FAS.

Safety Analysis Set (SAF): The SAF will comprise all patients in the IS who are administered with at least one dose of investigational drug during the treatment period.

Per Protocol Set (PPS): The PPS will comprise all patients in the FAS without any major protocol deviation.

Analysis sets for specific outputs are given in [Table 2-2](#).

Table 2-2 Analysis data sets for specific outputs

Table	IS	FAS	SAF	PPS
Concomitant medication			x	
Demographics and Baseline characteristics	x			
Exposure			x	
Medical history	x			
Other efficacy analyses		x		
Patient disposition	x			
Patient reported outcomes		x		
Primary and key secondary efficacy variables		x		x
Protocol deviations	x			
Safety analyses			x	

The number and percentage of patients in each analysis set will be summarized based on the IS.

If protocol deviations (PDs) occur, then the data from specific patients, visits, or evaluations may be excluded from analysis. The criteria and determination of clinically significant PDs leading to exclusion from PPS will be finalized prior to DBL and analysis.

2.2.1 Subgroup of interest

N/A

2.3 Patient disposition, demographics and other Baseline characteristics

2.3.1 Patient disposition

Patient disposition will be presented in listings.

The total number and percentage of subjects passing and failing screening be presented.

The number and percentage of patients who completed study periods (treatment period 1, treatment period 2, and extension treatment period) or discontinued the study prematurely including the reason for discontinuation will be presented by study periods for all subjects in the IS.

A schematic diagram of subject disposition will be provided.

2.3.2 Protocol deviations

The number and percentage of subjects with PDs will be tabulated by deviation category. A table with only major PDs and criteria leading to exclusion from analysis sets will also be presented. In both tables, subjects with multiple PDs will only be counted once at each level of summarization.

In addition, a listing of PDs will be produced including the accompanying deviation code.

Classification of which PDs will lead to exclusion from analysis sets will be agreed and documented in a data review meeting prior to database lock.

2.3.3 Demographics and other Baseline characteristics

Descriptive statistics for the following data and will be provided (including Baseline values of the main efficacy endpoints) for the IS population.

Demographics and background characteristics:

- age (in years, and year categories ≤ 65 , > 65)
- gender (male/female)
- child bearing status (able to bear children/post menopausal/sterile - of child bearing age)
- race (Caucasian/Black/Asian/native American/Pacific islander/other)
- smoking status (never/current/former)
- average pack year (former/current/overall)
- height (cm)
- weight (kg)
- body mass index (BMI) = weight (kg) / (height (meters))²
- sitting pulse (bpm)
- systolic and diastolic blood pressure (mmHg)
- pregnancy test (negative/positive/not done/unknown)
- education level (none/primary education/secondary education/university)

Disease history and Baseline disease characteristics:

- total body surface area (BSA) affected
- Baseline PASI
- time since diagnosis of plaque type psoriasis (years)
- Baseline Investigator Global Assessment (IGA)
- Baseline saPASI
- previous exposure to psoriasis therapy

The following data will also be summarized:

- standard 12-lead Electrocardiogram (ECG) at Baseline.
- QuantiFERON®-TB Gold In-Tube assay (QFT) at screening (positive / negative / indeterminate)
- X-ray (or Magnetic resonance imaging (MRI), computerized tomography (CT) scan) at screening

2.3.4 Medical history and current medical conditions

Analysis of medical history and current medical conditions will be based on the IS. General medical history, and current medical conditions collected in the CRF will be coded using the

Medical Dictionary for Regulatory Activities (MedDRA) dictionary. They will be summarized by system organ class (SOC) and preferred term (PT) of the MedDRA dictionary.

Psoriasis specific medical history will be summarized by predefined types of psoriasis collected on the CRF where the number and percentage of patients with each type will be presented. In addition, time since diagnosis will be summarized for the following categories: ≤ 1 year, > 1 and ≤ 5 years, < 5 and ≤ 10 years, < 10 and ≤ 20 years, and > 20 years.

2.4 Treatments (study treatment, rescue medication, concomitant therapies, compliance)

2.4.1 Study treatment

The analysis of study treatment data will be based on the SAF.

Duration of exposure is defined as the time from first dose of study treatment to the time of end of study day. For subjects who discontinue this will be the last visit in the corresponding treatment period. The duration of exposure to study treatments (days) will be calculated as:

$$\text{end of study date} - \text{start date of study treatment} + 1$$

The duration in days will be summarized using frequencies and percentables for categories: ≤ 4 weeks, $> 4 \leq 16$ weeks, $> 16 \leq 52$ weeks, $> 52 \leq 72$ weeks, and > 72 weeks.

The number of percentage of subjects with dose amount $< 300\text{mg}$, 300mg , and $> 300\text{mg}$ will be provided.

2.4.2 Prior, concomitant and post therapies

Prior or concomitant medication will be identified based on recorded or imputed start and end dates of medication taken. Prior (or previous) medication is defined as a treatment taken but stopped prior to first administration of investigational drug. Concomitant medication is any medication administered at least once between the day of first injection of investigational drug and the last day of study visit, including a medication initiated pre-screening and ongoing at the start of the treatment period.

Medications will be identified using the Novartis Drug and Therapy Dictionary (NovDTD) including Anatomical Therapeutic Chemical (ATC) code. Prior and concomitant treatments will be summarized for the SAF.

Prior and concomitant medications will be summarized in separate tables. They will be presented for the whole study period.

Medications will be presented in alphabetical order, by PT and grouped by anatomical main group. Tables will also show the overall number and percentage of patients receiving at least one treatment of a particular PT and at least one treatment in a particular anatomical main group.

By-patient listings for prior and concomitant medications will be provided.

Prior psoriasis therapy will be summarized overall, by type and PT.

2.5 Analysis of the primary objective

The primary objective is to evaluate the benefit of secukinumab on the severity of psoriasis based on the severity component of the SPI at Week 16.

2.5.1 Primary endpoint

The co-primary variables are:

- change from Baseline in proSPI (s) Week 16
- change from Baseline in saSPI (s) at Week 16

The primary analysis will be based on the FAS.

2.5.2 Statistical hypothesis, model, and method of analysis

The following hypothesis will be tested for each co-primary endpoint at the 5% significance level (2-sided):

$$H_0: \mu_d = 0$$

$$H_A: \mu_d \neq 0$$

where μ_d denotes the mean difference of paired observations.

To assess the primary objective, the absolute change from Baseline in proSPI (s) and absolute change from Baseline in saSPI (s) will be analyzed using a paired t-test (Week 16 vs Baseline).

The key assumptions underlying the use of a paired t-test will be checked. In the event the data is non-normal, Wilcoxon signed rank test will be performed.

An adjustment for multiplicity will be performed using the Hochberg procedure and the family-wise type-I-error will be set to $\alpha=5\%$ (2-sided). The adjustment will be applied as follows; if the maximum of the two p-values is rejected at the 5% level (2-sided) then both hypotheses are rejected and statistical significance is claimed for both endpoints. Otherwise if the maximum of the two p-values is not rejected, then the minimum p-value is tested at the 2.5% level (2-sided), if rejected then statistical significance is claimed only for this endpoint.

Descriptive statistics of proSPI (s) and saSPI (s) (Baseline, actual value, absolute and percentage change from Baseline) will be presented by visit for severity score and its components 1A and 1B. The number and percentage of reponses for 1A will be presented by body part. The change from Baseline of proSPI (s) and saSPI (s) will be presented graphically, showing the mean and SE of the change per visit.

The number and percentage of proSPI (s) and saSPI (s) will be presented by visit and by the following score bands: from 0 to 10, > 10 and ≤ 20 , > 20 and ≤ 30 , > 30 and ≤ 40 , > 40 and ≤ 50 . Graph of reponse distribution of proSPI (s) and saSPI (s) will be presented by the aforementioned score bands at Week 16.

2.5.3 Handling of missing values/censoring/discontinuations

Missing data will be imputed using Last Observation Carried Forward (LOCF) method. This approach will consist of replacing the missing Week 16 assessment by the last non-missing assessment value.

2.5.4 Supportive/sensitivity analyses

To assess for robustness of the results, the same analysis as specified in [Section 2.5.2](#) will be repeated for the FAS (on observed data).

The primary analysis for the two co-primary endpoints will be also be performed on the PPS.

2.6 Analysis of the key secondary objective

The key secondary objectives of this study are:

- to assess PASI weekly from week 0 to 4 then every 4 to 8 weeks until end of study
- to evaluate correlation between PASI and proSPI (s)

2.6.1 Key secondary endpoint

The key secondary variables are:

- absolute PASI score values at each post-Baseline visit until end of study
- the correlation coefficient between PASI and proSPI (s) at each post-Baseline visit

The key secondary endpoints analyses will be based on the FAS (observed data only).

2.6.2 Statistical hypothesis, model, and method of analysis

Descriptive statistics of PASI score (Baseline, actual value, absolute change and percentage change from Baseline) will be presented by visit. The percentage change from Baseline of these scores will be presented graphically, showing the mean and SE of the percentage change per visit. The number and percentage of PASI score will also be presented by body region, symptom, and visit.

The number and percentage for each PASI response category (PASI 50 responders, PASI 75 responders, PASI 90 responders, and PASI 100 responders) will be presented by visit. For example, PASI 50 responders are the patients achieving $\geq 50\%$ improvement (reduction) in PASI score compared to Baseline.

Change from Baseline to Week 16 of PASI score will be analyzed as for the primary analysis described in [Section 2.5.2](#).

For the evaluation of the correlation between PASI and proSPI (s) at each post-Baseline visit using Spearman's correlation coefficient. Scatterplots of PASI and proSPI(s) at Week 16 will also be provided.

2.6.3 Handling of missing values/censoring/discontinuations

Analysis and presentations of key secondary objectives will only be based on observed data.

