1.1 Study design

This is an open-label multicenter, single arm study in 120 patients with moderate to severe psoriasis. There will be no randomization nor interim analysis for this study.

[figure not shown]
The study consists of five epochs:

- Screening to occur between day -28 and day -7
- Treatment
 - Treatment period 1
 - Treatment period 2
- Extension treatment period
- Follow-up

There will be an initial induction phase (5 weekly injections) before switching to monthly injections until Week 16. The patient will continue with monthly injections until Week 48 in case of a favorable response to treatment at Week 16. Patients who are deemed to be benefiting from the study drug after 48 weeks of treatment could be continuously treated until 3 November 2016 or until commercialization of Cosentyx[®] in France, whichever occurs first.

An illustration of the study design is depicted in [Figure 1.1](#).

Figure 1-1 Study design

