1.2.2 Secondary objectives

Key secondary objectives are:

- ✓ to assess Psoriasis Area and Severity Index (PASI) weekly from week 0 to 4 then every 4 to 8 weeks until Week 56
- ✓ to evaluate correlation between PASI and proSPI (s)

Other secondary objectives include:

- ✓ to assess proSPI (s, p and i) over time (weekly from Week 0 to Week 4 then every 4 to 8 weeks until Week 56).
- ✓ to assess saSPI (s, p and i) over time (weekly from Week 0 to Week 4 then every 4 to 8 weeks until Week 56).
- ✓ to assess Dermatology Life Quality Index (DLQI) over time (weekly from Week 0 to Week 4 then every 4 to 8 weeks until Week 56).
- ✓ to assess self-administered PASI (saPASI) (weekly from Week 0 to Week 4 then every 4 to 8 weeks until Week 56).
- ✓ to assess pain, itching, and scaling using the Psoriasis Symptom Diary questionnaire over time (weekly from Week 0 to Week 4 then every 4 to 8 weeks until Week 56).

- to evaluate correlation between proSPI (for each component separately: s, p, i) and DLQI
- to evaluate correlation between proSPI (p, i separately) and PASI
- to evaluate safety during the treatment period (until the Week 52) and during the extension treatment period (after the Week 52)

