2.1 Data analysis general information

The analysis will be performed by Novartis. The statistical software used for the analyses will be SAS version 9.4 or later.

Descriptive statistics for continuous variables in the study will include the number of observations, mean, standard deviation (SD), median, minimum, and maximum. The following number of decimal places will be used: mean, and median, values to 1 more decimal place than the raw data; minimum and maximum to the same number of decimal places as the raw data and SD to 2 more decimal places than the raw data.

For categorical variables frequency and percentage will be presented for non-missing data.

If appropriate, 95% Confidence Intervals (CIs) will be presented along with p-values.

Unless otherwise specified, all statistical tests will be two-sided and will use the 5% level of significance.

All data will be listed by patient unless stated otherwise.

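### Responder percentages after Week 16 are planned on observed data only, although continuing depends on response, so they can be expected to overstate the rate in the full FAS.

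*SAP*

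**What the plan says.** **Who continues.** SAP 1.1 states: "The patient will continue with monthly injections until Week 48 in case of a favorable response to treatment at Week 16". It then adds a second selection: "Patients who are deemed to be benefiting from the study drug after 48 weeks of treatment could be continuously treated". That extension runs "until 3 November 2016 or until commercialization", whichever comes first. SAP 1.2.2 puts the boundary between the treatment period and the extension at Week 52.

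**What is tabulated.** SAP 2.6.2 gives counts and percentages of PASI 50, 75, 90 and 100 responders by visit. SAP 2.7.2 does the same for a DLQI of 0 or 1.

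**On which data.** For PASI, SAP 2.6.3 says: "Analysis and presentations of key secondary objectives will only be based on observed data". For DLQI, SAP 2.7 restricts the analysis to observed data in the FAS and 2.7.3 rules out replacing missing values. SAP 2.1 fixes the denominator: "For categorical variables frequency and percentage will be presented for non-missing data".

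**What could bring stopped patients back in.** Follow-up visits are not mapped to visit windows (2.1.1.4), and 2.1.1.5 says: "Efficacy data collected at follow up visits will not be summarized". Unscheduled visits are treated differently in 2.1.1.6: "Efficacy data collected at unscheduled visits will be visit windowed as per section 2.1.1.4". The supportive analysis for the key secondary objective (2.6.4) is given as N/A.

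**The concern.** Whether a patient still has PASI and DLQI values after Week 16 depends, by design, on how that patient had responded. A percentage over non-missing values at Week 24 or later then has the patients with the poorest response largely removed from both numerator and denominator. The table would carry the FAS label but describe a subset selected on response.

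The trial has one arm and no control, so the curve of responder rates over visits is a natural way to read whether the effect lasts. A rate that holds or rises after Week 16 could come partly from who is left. LOCF in 2.5.3 covers only the missing Week 16 SPI value. The PPS run in Table 2-2 uses a subset of the FAS under the same observed-data rule. Neither addresses the later visits.

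**Working it through.** **Inputs.** From the SAP: 120 patients planned (1.1 and Section 3), taken here as the FAS size; continuation by response (1.1); non-missing denominator (2.1). The SAP has no figure of its own for this point: it gives neither a stopping rate after Week 16 nor an expected responder rate. The drop-out of 20 in Section 3 serves to inflate 100 evaluable patients to 120 for the primary analysis and is not a stopping rate after Week 16. The following are therefore assumptions:

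- *k*, number stopped, with *f* = *k*/120
- *r*, responder rate in those continuing
- *r0*, rate that stopped patients would show at the same visit
- *u*, number of stopped patients with a windowed unscheduled value

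**Step 1: no later values from stopped patients.** The observed rate is *r*. The full-FAS rate is (1 − *f*)·*r* + *f*·*r0*. The gap is *f*·(*r* − *r0*), which is positive whenever stopped patients respond less often than those continuing. With *r* = 80%, in percentage points:

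| *k* of 120 | *r0* = 0 | *r0* = 20% | *r0* = 30% |
|---|---|---|---|
| 5 | 3.3 | 2.5 | 2.1 |
| 10 | 6.7 | 5.0 | 4.2 |
| 20 | 13.3 | 10.0 | 8.3 |
| 30 | 20.0 | 15.0 | 12.5 |

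For example, with 20 stopped and *r0* = 30%: (20/120) × (80 − 30) = 8.3. Letting *r* run from 70% to 90% over the same *k* and *r0* gives 1.7 (5/120 × 40) to 22.5 points (30/120 × 90).

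**Step 2: some stopped patients return through unscheduled visits.** Observed = [(120 − *k*)·*r* + *u*·*r0*]/(120 − *k* + *u*); full FAS = [(120 − *k*)·*r* + *k*·*r0*]/120. With *k* = 20, *u* = 5, *r* = 80%:

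- *r0* = 0: 80/105 = 76.2% against 80/120 = 66.7%, gap 9.5
- *r0* = 20%: 81/105 = 77.1% against 84/120 = 70.0%, gap 7.1
- *r0* = 30%: 81.5/105 = 77.6% against 86/120 = 71.7%, gap 6.0

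The gap shrinks but does not close.

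**Step 3: what a reader could recover from the planned tables.** Responder count over FAS size gives a crude bound. Suppose 20 stopped, 5 are still in the study but not assessed at the visit, and 76 of the 95 observed respond:

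- observed: 76/95 = 80.0%
- crude bound: 76/120 = 63.3%
- stopped counted as non-responders, not assessed excluded: 76/115 = 66.1%

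The bound lies 2.8 points below the last figure because it treats a missed visit like a stop for lack of response.

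**The case against.** The SAP states its observed-data basis openly and never claims that these percentages estimate a full-FAS rate. Response among patients still assessed is a legitimate descriptive quantity. The responder rates stand in neither endpoint list (2.6.1, 2.7.1), carry no test and drive no decision. The continuous summaries must show the number of observations (2.1), and disposition with reasons is reported by period (2.3.1), so a careful reader can get near the missing figure. SAP 1.1 conditions injections, not visits: the SAP does not say that patients who stop have no later assessments, and it does not define a favorable response. If few fail that condition, or if stopped patients keep attending, the gap is close to zero. Counting stopped patients as non-responders also has its own bias: with 20 stopped, *r* = 80% and *r0* = 30%, the full-FAS rate is 71.7%, while this convention gives 80/120 = 66.7%, which is 5.0 points too low.

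Most of this stands as a limit on the finding. The outputs are descriptive, the absence of later visits is an inference, the size is unknown, and the convention brackets the target without recovering it. The same selection also acts on the by-visit mean PASI, which the proposed table does not change.

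The objection does not supply a by-visit FAS rate that separates stopped from unassessed patients. Disposition is by period and in the Included Set, so it cannot make that split at a visit. Stating the observed-data basis also does not tell the reader that, after Week 16, missingness is tied to response by the design itself.

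**Conclusion.** The concern holds. The SAP combines continuation by response with by-visit responder percentages over non-missing values, keeps follow-up efficacy out of the summaries, and plans no full-FAS counterpart. After Week 16 the PASI 50/75/90/100 and DLQI 0/1 percentages can be expected to overstate the full-FAS rate.

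The direction is expected, not certain. It requires that patients who stop respond less often than those who continue and that few of them have later windowed values. The size cannot be found from the SAP. In the illustrations at 80% response in continuers it runs from 2.1 to 20.0 points for 5 to 30 of 120 stopped, and from 6.0 to 9.5 points if 5 of 20 stopped patients are still observed. The Week 16 co-primary tests and the Week 16 PASI test are not affected. This should be fixed, but it does not threaten the trial's main conclusion.

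**What to change.** Replace N/A in 2.6.4, and add to 2.7.3, a supportive table of PASI 50/75/90/100 and DLQI 0/1 at Weeks 24, 32, 40, 48 and 52 with the full FAS as denominator, under these rules:

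1. Any evaluable value in the visit window is used as observed, including one from the stopping visit or an unscheduled visit.
2. A patient with no evaluable value who prematurely discontinued the study or study treatment before that visit's scheduled day in Table 2-1, including for lack of favorable response at Week 16, counts as a non-responder.
3. A patient who completed treatment to Week 48 as planned is not treated as stopped.
4. Every other patient without an evaluable value goes in a separate row for not assessed and stays in the denominator. The rate is also given with these patients excluded.

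Keep the observed-data tables, show n beside each responder percentage, and label those after Week 16 as conditional on continuing. The same label can be carried to the by-visit mean PASI tables. Show extension visits only as conditional on entering the extension, without non-responder imputation, because the extension can end on a calendar date or at commercialization.

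The cost is SAP wording, table labels and one extra set of tables, with no new assessments. Rule 2 needs the date of treatment discontinuation as well as study discontinuation; 2.3.1 mentions only the latter, so the team should confirm that the former is in the database. The added rates will look less favourable, and the text should say that counting stopped patients as non-responders is a convention.
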